Subjects (1) who complete the 5-day treatment, (2) who are still hospitalized upon treatment completion, (3) who are on invasive mechanical ventilation or who have an ongoing respiratory deficiency as evidenced by having a peripheral capillary oxygen saturation (SpO₂) <94% on room air, or in case of known pre-influenza SpO₂ <94% (eg, due to COPD), the current blood oxygen saturation on room air is lower than pre-influenza infection levels by at least 3%, (4) who, in the opinion of the investigator, are expected to derive clinical benefit from extending the treatment period, and (5) for whom the investigator agrees to extend treatment with the same SOC will be given the option for treatment extension. In the second blinded course of treatment, subjects will continue treatment with pimodivir or placebo for another 5 days in combination with continued SOC treatment. If the SOC contained no influenza antiviral during the first treatment period, no influenza antiviral can be started in the treatment extension as part of the SOC

[figure not shown]
The study will consist of a screening/baseline visit, a double-blind treatment period of 5 days (with the possibility to extend the treatment period), and a follow-up period of 23 days after the last dosing day. The entire study duration for each subject will be 28 days, except for subjects receiving extended treatment, for whom the study will last 33 days. The study is considered complete with the completion of the last study assessment for the last subject participating in the study.

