2.1.1. Phase Definitions

Table 1: Construction of phases

Trial phase	Trial subperiod ^{*1}	Start date	End date
Screening (phase 1)		The date of signing the informed consent with 00:00 as a timepart	1 minute before the first study drug intake
Treatment (phase 2)		Datetime of first study drug intake ^{*4}	Datetime of last study drug intake ^{*4} + 24 hours
	Planned Treatment (subperiod 1) ^{*2}	Datetime of first study drug intake ^{*4}	If extended treatment then Datetime of first study drug intake in extended treatment subperiod – 1 minute Else Datetime of last study drug intake ^{*4} + 24 hours
	Extended Treatment (subperiod 2) ^{*3}	Datetime of first study drug intake in extended treatment subperiod ^{*4}	Datetime of last study drug intake ^{*4} + 24 hours
Follow-up (phase 3)		End of the treatment phase +1 minute	Trial termination date (or date of last contact if later)

^{*1}: A treatment period will be constructed in the derived datasets with the same start and end date as the treatment phase.

^{*2}: The planned treatment subperiod will be present for all treated subjects.

^{*3}: The extended treatment subperiod will only be present for all subjects with extended treatment.

^{*4}: In case the time part of the study drug intake is missing the imputed time part will be used as described below.

Additionally, the treatment phase and follow-up phase will be combined in the analysis.

In case the time part of first study drug intake is missing the randomization time will be used. In case the time part of the randomization time is also missing we impute the time part with 8:00 if taken in the morning or with 20:00 if study drug was taken in the evening. In case the time of the last study drug intake is missing, the time part will be imputed with 8:00 if the last study drug was taken in the morning or with 20:00 if the last study drug was taken in the evening.

In case the time part of first intake of the treatment extension is missing, the time part will be imputed with 8:00 if the last study drug of the planned 5 days of treatment was taken in the morning or with 20:00 if the last study drug was taken in the evening.

The last phase, whichever it is for a subject, always ends on 23:59 of the day of trial termination (or date of last contact if later).

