5.1. Analysis Specifications

5.1.1. Level of Significance

The population used for the evaluation at the final analysis will depend on the outcome scenario of the interim analysis: i.e.; scenario 1: continue with the full study population or scenario 2: continue only with the subjects with an onset of symptoms less than 72 hours before first study drug intake. Tables/graphs/listings will account for the selected scenario.

As a confirmatory strategy, to account for multiplicity in the statistical evaluation of the most important efficacy endpoints, in either scenario, a combination of hierarchical testing and the Bonferroni-Holm testing procedure will be applied to control for the overall Type I error rate at the 5% level. The following endpoints are included in the confirmatory strategy:

1. Hospital recovery scale at Day 6, ie, primary endpoint
2. Incidence in post-baseline complications
3. Time to hospital discharge
4. Time from ICU admission to ICU discharge
5. Time to return to daily activities
6. Time from start of mechanical ventilation to end of mechanical ventilation
7. Rate of re-hospitalization

First, the primary endpoint will be tested for superiority of pimodivir in combination with SOC over placebo in combination with SOC at the 2-sided 5% significance level.

The confirmatory test procedure follows the Serial Gate Keeping strategy as outlined in Section 7 of the FDA's draft guidance on Multiple Endpoints to control the overall type I error at the 5% 2-sided level. The primary and six most important secondary endpoints (listed above) will be tested in the hierarchical order per the 5 steps outlined below. All alphas and p-values specified are 2-sided.

Step 1: Test the primary hypothesis ("Hospital recovery scale at Day 6")

- If the p-value is $\leq 5\%$, continue to Step 2.
- If the p-value is $> 5\%$, stop testing, and no claim will be made.

Step 2: Test first set of 2 secondary endpoints (“Incidence in post-baseline complications” and “Time from start of study drug to hospital discharge”). The Bonferroni-Holm procedure will be applied to control the type I error within Step 2.

- If the smallest of the 2 p-values is $\leq 2.5\%$ and the largest of the 2 p-values is $\leq 5\%$, continue to Step 3.

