Incidence of treatment-emergent adjudicated influenza complications	
The incidence of treatment-emergent adjudicated influenza complications from first study drug intake until the end of the study will be categorized in a hierarchical fashion. The incidence will be presented for the overall category, for the subcategories and for each adjudicated complication within a subcategory.
 
The overall category will consist of any adjudicated complication.
 
The following subcategories are defined:
 
 • Pulmonary complications: 
 ○ respiratory failure, ○ primary viral pneumonia, ○ secondary bacterial pneumonia, ○ exacerbations of chronic underlying pulmonary diseases, ○ bronchitis ○ other complications • Extrapulmonary complications: 
 ○ Cardiovascular and cerebrovascular disease (eg, myocardial infarction, congestive heart failure, arrhythmia, stroke), ○ Muscular disorders (eg, myositis, rhabdomyolysis), ○ Central nervous system (CNS) involvement, ○ Acute exacerbation of chronic kidney disease, ○ Decompensation of previously controlled diabetes mellitus, ○ Other infections (eg, sinusitis, otitis) ○ Other complications • Pulmonary complications including sinusitis and otitis • Major / minor complications • Infectious / non-infectious complications 
The complications sinusitis and otitis are determined based on their MedDRA preferred terms as listed in Attachment 1, table 6, for the protocol terms ‘Sinus infection’ and ‘ear infection’ respectively. Only if those terms are judged to be complications by the adjudication committee they will be included for the endpoint ‘Pulmonary complications including sinusitis and otitis.’

Incidence of not being hospitalized on Day 6.	On Day 6 (relative day) subject is in the hospital at least a part of the day (‘Yes’) or the subject is not in the hospital during the whole day (‘No’).
Incidence of hospital readmission	Does the subject require hospital readmission after first discharge (The start date of the hospital readmission must be at least 1 day in between the end of the previous hospitalization)? Categories will be Yes (1) or No (0).

Incidence of all-cause mortality	
Did the subject die after first dose of study drug?
 
Categories will be Yes (1) or No (0).

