Bootstrapping with replacement, considering also the actual proportion of subjects in each stratum, will be used to obtain a 100% sample size 10001 times. The median (95% CI) time-to event will be derived from the 10001 bootstrapped samples.

Cox Proportional Hazard model

A stratified Cox proportional hazards model will be used adjusted for the stratification factors and for the time from admission to start of treatment (for the time to hospital discharge and time to hospital discharge readiness),. The hazard ratio for the comparison of pimodivir versus placebo will be reported together with the 95% confidence interval. A Log-log plot of survival will be added to check the proportional hazard assumption of the Cox proportional hazards model.

For the subgroup analyses the Log-Log plot of survival will be shown for each subgroup category separately.

Logistic regression model

A logistic regression model (Firth's penalized likelihood approach), with treatment group and stratification factors as fixed effects, will be used to analyze binary outcomes and to obtain the odds ratios (95% CI) for the comparison of pimodivir versus placebo.

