7.1. Adverse Events

7.1.1. Definitions

Coding of AE

The verbatim terms used in the eCRF by investigators to identify AEs will be coded using the Medical Dictionary for Regulatory Activities. Events are looked at on the level of their preferred term.

Treatment-emergent AE

Pre-treatment AEs are defined as AEs that were reported or worsened after signing the ICF up to the start of study drug dosing. Treatment-emergent AEs (TEAE) are defined as AEs that were reported or worsened on or after the start of study drug dosing and up to and including the end of the follow-up phase.

An AE, at the preferred term level, is considered treatment-emergent if:

- an AE starts after or at first dose of study drug and
 - o The AE was not present prior to first dose of study drug
- an AE was present prior to first dose of study drug:
 - the same AE (based on preferred term) starts at the end date or the day after the end date of the AE present prior to first dose and new AE has worsened, ie an increase in toxicity grade or changed to an SAE
 - the same AE (based on preferred term) started 2 or more days after the end date of the AE present prior to first dose
- The start date of the AE is missing
- The start time of the AE is missing, and the AE was not present the day before first dose of study drug, and the start date of the AE is the same as the start date of first dose of study drug
- The day is missing of the AE start date but month and year are the same as month and year of first study drug intake.
- The month is missing of the AE start date but the year is the same as the year of the first study drug intake.

Phase allocation of AE

Adverse events present in the SDTM database are allocated to phases based on their start date and time. If the start date and time of an event falls between (or on) the start and stop date and time of a phase, the AE is attributed to that phase (treatment-emergent principle).

Rule: phase start datetime \leq AE start datetime \leq phase stop datetime.

Incomplete AE dates and or times (i.e. time and/or day and/or month and/or year missing):

- In case of partial AE start dates and or times, the events are allocated to the phases using the available partial information on start and end datetime; no imputation will be done. If, for instance, for the AE start date only month and year are available, these data are compared to

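### Complications (confirmatory endpoint 2) are counted to Day 28 or Day 33 depending on a post-randomization treatment extension, with no common cut-off day; the resulting bias is small, can go either way, and is cheap to remove

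*SAP*

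**What the plan says.** SAP 5.1.1 lists "Incidence in post-baseline complications" second in the confirmatory sequence and re-hospitalization seventh. SAP 5.3.1.1 gives their counting rules, and that for all-cause mortality, which is a secondary endpoint outside the sequence:

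- Complications are counted "from first study drug intake until the end of the study".
- Readmission asks "Does the subject require hospital readmission after first discharge", with no last day.
- Mortality asks "Did the subject die after first dose of study drug", with no last day.

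Protocol 3.1 sets participation at 28 days, "except for subjects receiving extended treatment, for whom the study will last 33 days". Treatment-emergent adverse events, from which complications are adjudicated, run "up to and including the end of the follow-up phase" (SAP 7.1.1). Under SAP 2.1.1 that phase closes at the subject's own termination date, or at last contact if that is later.

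SAP 5.3.2 says a Firth-penalized logistic regression, "with treatment group and stratification factors as fixed effects, will be used to analyze binary outcomes". SAP 5.3.2.1 puts every subject in the analysis set in the denominator. We found no common cut-off day and no term for length of follow-up.

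Protocol 4.3 offers extension to subjects who have completed the 5-day course, are still hospitalized, and are ventilated or still have low oxygen saturation, subject to investigator judgment. The proportion extended is itself a secondary endpoint (Protocol 2.1.2).

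**The concern.** A yes/no incidence is comparable between arms only if the arms are observed over the same period. Here the last five days are opened only for subjects who were doing poorly at the end of the first course. That status is measured after randomization and could be affected by the drug. If pimodivir speeds recovery, fewer of its subjects are extended, and placebo has more subject-days in which a complication can be counted. Part of any observed difference would then come from length of follow-up.

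Endpoint 2 is tested only after the primary endpoint succeeds, which is the setting in which extension rates are most likely to differ. Together with time to hospital discharge it forms the first Holm pair, so it can support a claim on its own at 2.5%.

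**Working it through.** **The plan's own figure.** Protocol 11.3 gives 600 subjects for 90% power at a common odds ratio of 0.62 (38% reduction), with placebo Day 6 shares of 30/30/25/5/5/5%. The Whitehead formula is N = 12(z0.975 + z0.90)² / [ln(OR)² × (1 − Σp̄³)], where p̄ is the mean share of each category over the two arms. With 1 − Σp̄³ = 0.9175 it gives N = 601.4, and 89.9% power at N = 600. The figure is reproduced, so the same Day 6 distribution is used below. The documents give no power calculation for endpoints 2 or 7.

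**Extension shares.** Actual extension rates are not in the documents. As a high case, assume every subject in categories 3 to 5 on Day 6 is extended.

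- Placebo: 25 + 5 + 5 = 35%.
- Pimodivir, category 3 or worse: odds 0.62 × 0.40/0.60 = 0.413, or 29.25%. Death: odds 0.62 × 0.05/0.95 = 0.0326, or 3.16%. Difference: 26.1%.

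Mean planned follow-up is 28 + 5e days, where e is the extended share. That is 29.75 days on placebo and 29.30 on pimodivir, a gap of 0.45 day.

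**Effect on endpoint 2 with no true effect on complications.** Incidence per arm = e × [1 − exp(−33L)] + (1 − e) × [1 − exp(−28L)], with the same constant hazard L in both arms. For base incidence, take 15.6% by Day 28 as an assumption; it is the placebo-arm rate (5/32) that Protocol 1.1 reports for the earlier hospital study.

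- L = −ln(1 − 0.156)/28 = 0.00606 per day, so 33-day incidence is 18.1%.
- Placebo: 0.35 × 0.1812 + 0.65 × 0.156 = 16.48%.
- Pimodivir: 0.261 × 0.1812 + 0.739 × 0.156 = 16.26%.
- Difference 0.22 points; odds ratio 0.984.
- Rejection at two-sided 5%, 300 per arm, normal approximation: 5.06%.

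This is a plain two-arm comparison. It ignores covariates, the Holm split and the stage-wise combination of p-values.

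**Range.** The first row takes the Day 29-33 hazard as a quarter of the average; the others hold it constant.

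| Extended, placebo vs pimodivir | 28-day incidence | Odds ratio | Rejection |
|---|---|---|---|
| 35% vs 26.1%, late hazard one quarter | 15.6% | 0.996 | 5.00% |
| 35% vs 26.1% | 5% to 26.7% | 0.983 to 0.985 | 5.02% to 5.11% |
| 35% vs 15% (assumed) | 5% to 26.7% | 0.961 to 0.966 | 5.1% to 5.5% |
| Equal | any | 1.000 | 5.00% |
| 26.1% vs 35% (reversed) | 15.6% | 1.017 | 5.06% |

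With a common Day 28 end, the window-only difference is exactly zero in every row.

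If extended subjects have twice the hazard (15.6% for the others, 35% vs 26.1% extended), the odds ratio is 0.911 as written and 0.928 with a Day 28 end. Only the step between those two comes from the window. The rest reflects the assumed difference in how many high-hazard subjects each arm has.

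**Endpoint 7.** Time at risk for readmission starts at first discharge.

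| Subject | First discharge | Days at risk |
|---|---|---|
| Not extended | Day 4 | 28 − 4 = 24 |
| Extended | Day 6 | 33 − 6 = 27 |
| Extended | Day 12 | 33 − 12 = 21 |

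The extended subject has longer at risk only if discharged less than five days later than the comparator.

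**The case against.** The strongest reply is that the effect is negligible. On the plan's own assumptions it moves the rejection rate from 5.0% to about 5.06%, and that assumes everyone in categories 3 to 5 is extended, although Protocol 4.3 also requires expected benefit and agreement to continue the same standard of care. No passage shows that the hazard four weeks after first dose is as high as the 28-day average. The documents set out to investigate extension and do not say that it is expected to differ by arm. This stands, and it limits the point to a cheap improvement.

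Protocol 3.1 also gives every subject 23 days of follow-up after the last dosing day, so post-treatment observation is equal by design. Complications are tabulated by phase and subperiod (SAP 7.1.2), and treatment extension is a subgroup for efficacy (SAP 2.3). These displays show where events fall, but they do not change the confirmatory test, which counts from first dose.

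A reader might infer that endpoint 7 is biased in the same direction. The documents do not support that: readmission can occur only after first discharge, and extended subjects are still in hospital when the first course ends, so their time at risk may be longer or shorter.

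A reader might also group mortality with the error-controlled endpoints. It is not in the confirmatory sequence, and SAP 5.3.1.1 already tabulates cumulative deaths per day, so Day 28 mortality can be read off descriptively.

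**Conclusion.** The point holds for endpoint 2. Its counting window is 28 or 33 days according to a post-randomization clinical decision, and neither the model nor the denominator corrects for this. If fewer pimodivir subjects are extended, the bias favours pimodivir. Its size is an odds ratio of about 0.98 and a rejection rate of about 5.06%, given 35% vs 26.1% extended, a constant hazard and 15.6% base incidence. It is smaller if the late hazard falls, zero if extension is equal, and reversed if more pimodivir subjects are extended. Extension rates and the Day 29-33 hazard are assumptions.

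For readmission and mortality the gap is the missing end day. The unequal end follows from that silence, and for readmission no direction is established. The calculations do not support a claim of material type I error inflation under the plan's planning assumptions. The reason to act is that a confirmatory endpoint should have one window for everyone, and that supplying one costs little.

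**What to change.** In SAP 5.3.1.1, define the confirmatory complications endpoint as adjudicated events with onset from first dose through Day 28 for every subject, whether or not treatment was extended. Use the same Day 28 end for readmission and all-cause mortality, so that all three share one window from first dose. Report Day 29-33 events in extended subjects in supportive and safety displays. Make the change before unblinding, and apply it to both the pre-interim and post-interim p-values that SAP 5.1.2 combines.

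The cost is SAP wording and a date condition in programming. Planned follow-up already reaches Day 28 for everyone, apart from withdrawals and the one-day window around the post-discharge final visit. The downside is that a few late events leave the efficacy comparison.

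For readmission, the common end equalizes the window from first dose but not the time at risk after discharge: an extended subject discharged on Day 12 would have 28 − 12 = 16 days at risk, down from 21. The report should say so when interpreting that endpoint.

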 - To investigate the number (proportion) of subjects requiring re-hospitalization in the pimodivir in combination with SOC treatment arm, compared to the placebo in combination with SOC treatment arm.
 - To investigate the number (proportion) of subjects not hospitalized at Day 6 in the pimodivir in combination with SOC treatment arm, compared to the placebo in combination with SOC treatment arm.
 - To investigate the time to clinical response in the pimodivir in combination with SOC treatment arm, compared to the placebo in combination with SOC treatment arm.
 - To investigate the time to improvement of respiratory status in the pimodivir in combination with SOC treatment arm, compared to the placebo in combination with SOC treatment arm.
 - To assess the PK of pimodivir and to explore the PK/PD relationships of pimodivir for efficacy and safety.
 - To investigate the acceptability (taste and swallowability) of the pimodivir formulation in adolescents.
 - To evaluate superiority with respect to the following influenza A viral parameters in the pimodivir treatment arm compared to the control arm by qRT-PCR and viral culture:
 - Time to viral negativity.
 - Viral load over time.
 - To investigate the emergence of viral resistance against pimodivir detected by genotyping and/or phenotyping.

Exploratory Objective

- To evaluate the measurement performance of the influenza symptom diary for hospitalized influenza subjects.

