2.1.2. Endpoints

Primary Endpoint

The primary endpoint is the hospital recovery scale as assessed on Day 6.

Secondary Endpoints

The secondary endpoints are:

- Safety and tolerability based on assessment of AEs, clinical laboratory assessments, 12-lead electrocardiograms (ECGs), vital signs, and peripheral capillary oxygen saturation.
- Time from start of study drug to hospital discharge and total length of hospital stay.
- Time from ICU admission to ICU discharge and total time in ICU. Time in ICU before start of study drug is discarded.
- Time from start to end of mechanical ventilation and total time on mechanical ventilation. Time on mechanical ventilation before start of study drug is discarded.
- The hospital recovery scale as assessed each separated day from Days 2 to 14 (excluding the primary time point).
- Time to return to daily activities.
- Incidence of complications associated with influenza after the start of study treatment:

- Pulmonary complications:

The pulmonary complications of influenza include respiratory failure, primary viral pneumonia, secondary bacterial pneumonia (including pneumonia attributable to unusual pathogens), exacerbations of chronic underlying pulmonary diseases such as COPD, asthma, and bronchitis.

- Respiratory failure: defined as either hypoxemic respiratory failure characterized by an arterial oxygen tension (PaO_2) lower than 60 mmHg with a normal or low arterial carbon dioxide tension (PaCO_2), or hypercapnic respiratory failure characterized by a PaCO_2 higher than 50 mmHg.
- Primary viral pneumonia: a progressive event involving the lower respiratory tract with bilateral and/or diffuse radiological findings. No bacterial agent is identified using sputum cultures.
- Secondary bacterial pneumonia (including pneumonia attributable to unusual pathogens): a clinical event compatible with lower respiratory tract involvement, with lobar infiltrates on radiological studies and/or microbiological isolate of a bacterial pathogen, including unusual pathogens.
- Exacerbations of chronic underlying pulmonary diseases such as COPD and asthma: subjects with documented medical history of COPD or asthma with a sudden worsening of symptoms and deteriorating respiratory function (the latter as evidenced by worsening hypoxia, tachypnea, etc.) The event must start before a full recovery from the influenza infection occurred.
- Bronchitis
- Extrapulmonary complications:

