 - Cardiovascular and cerebrovascular disease (eg, myocardial infarction, congestive heart failure, arrhythmia, stroke)
 - Muscular disorders (eg, myositis, rhabdomyolysis)

-
- Central nervous system [CNS] involvement
 - Acute exacerbation of chronic kidney disease
 - Decompensation of previously controlled diabetes mellitus
 - Other infections (eg, sinusitis, otitis)
 - All-cause mortality.
 - Incidence and duration of antibiotic treatment.
 - The number (proportion) of subjects needing extended treatment.
 - The number (proportion) of subjects requiring re-hospitalization.
 - The number (proportion) of subjects not hospitalized at Day 6.
 - Time to clinical response. Clinical response is defined as achieving 4 of the 5 following vital sign resolution criteria, including at least the fever and oxygen saturation criteria, maintained for at least 24 hours:
 - having no fever (without the use of antipyretics within 8 hours),
 - oxygen saturation of at least 94% without oxygen supplementation or return to pre-influenza infection oxygen saturation (in patients with a known pre-influenza oxygen saturation level <94%),
 - improved respiratory status (a respiratory rate ≤ 24 breaths per min without supplemental oxygen or return to pre-influenza infection supplemental oxygen requirement in patients with chronic oxygen use),
 - heart rate 100 beats per minute or lower,
 - systolic blood pressure of 90 mmHg or higher without inotropic support given within 2 hours of assessment.
 - Time to respiratory response. Respiratory response is defined as achieving the following 2 criteria for at least 24 hours:
 - improved oxygen saturation of at least 94% without oxygen supplementation (return to pre-influenza infection oxygen saturation in patients with a known pre-influenza oxygen saturation level <94%) and
 - improved respiratory status characterized by a respiratory rate ≤ 24 breaths per min without supplemental oxygen or return to pre-influenza infection supplemental oxygen requirement in patients with chronic oxygen use.
 - PK parameters of pimodivir (ie, plasma concentration just prior to the beginning or at the end of a dosing interval [C_{trough}], C_{max} , t_{max} , and AUC_{12h}), as determined by population PK analysis.
 - Time to viral negativity by qRT-PCR and viral culture.
 - Viral load over time by qRT-PCR and viral culture.
 - The emergence of viral resistance against pimodivir detected by genotyping and/or phenotyping.
-

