5.3. Major Secondary Endpoints

5.3.1. Definition

Formulae to be used for derived variables, including data conversions, are provided in the tables below.

Note that for time-to event variables the actual date or times that the endpoint is met will be used. For the time-to-event variables, in case of death prior to the event, the subject will be censored using a time-to equal to the maximum time across all subjects.

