5.3.2.1. Clinical outcome

Time-to event parameters for clinical outcome

The time-to event parameters for clinical outcome will be analyzed as described above using a stratified Gehan-Wilcoxon test, a stratified log-rank test, a Kaplan-Meier analysis, an accelerated failure time model and a Cox proportional hazards model. The Gehan-Wilcoxon test is the primary analysis for time-to-event parameters. The Kaplan-Meier analysis will provide the primary estimation of time-to-event.

Duration parameters

Descriptive statistics of the duration parameters will be shown for all subjects that had the specific event. e.g. only subjects admitted to ICU will be included in the total time in ICU analysis.

Total length of hospitalization, total time in ICU, total duration of antibiotics, and total time on mechanical ventilation will be analyzed by using the Hodges-Lehman approach. Corresponding 95% CIs will be presented as well.

Incidence parameters

For each parameter the number and percentage of subjects in each category and subcategory will be tabulated and listed. All Subjects in the applicable analysis set will be counted for the denominator of the proportion.

The occurrence (yes/no) as described for the incidence parameters will be analyzed using logistic regression as described above (Section 5.3.2).

The occurrence (yes/no) of influenza complications will be analyzed using logistic regression as described above for the following categories:

- the overall influenza complications
- the pulmonary complications,
- the extrapulmonary complications
- the infectious complications
- the non-infectious complications
- the major complications
- the minor complications
- the pulmonary complications including sinusitis and otitis

Hospital recovery scale outcome and fundamental hospital recovery scale outcome on Day 2 to 14

This parameter will be analyzed analogous to the primary endpoint: hospital recovery scale outcome on Day 6, but then for Day 2 to 14 with Day 6 excluded for the HRS and including Day 6 for the fundamental HRS. The proportional odds model will be applied, and the proportional odds assumption will be tested for the treatment effect. The same 5 dichotomization of the HRS will be analyzed using a logistic regression model. Also, similarly as the primary endpoint the Van Elteren test will be provided in case the proportional odds assumption is not valid. The MI analysis will not be applied.

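### Two SAP 5.3.1.1 derivations are wrong as printed: the Day 6 not-hospitalized endpoint is coded backwards with no death rule, and total hospital stay is overcounted for readmitted subjects

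*SAP*

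**What the plan says.** **Day 6 status.** Protocol 2.1.2 lists as a secondary endpoint "The number (proportion) of subjects not hospitalized at Day 6". The matching objective in Protocol 2.1.1 is exploratory in tone: "To investigate the number (proportion) of subjects not hospitalized at Day 6". The row for this endpoint in SAP 5.3.1.1 is titled as the incidence of not being hospitalized. It gives 'Yes' if the "subject is in the hospital at least a part of the day" and 'No' if "the subject is not in the hospital during the whole day". It mentions neither death nor withdrawal.

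SAP 5.3.2.1 sends each incidence parameter, with its yes/no as described in the row, to logistic regression, and states: "All Subjects in the applicable analysis set will be counted for the denominator of the proportion". The general death rule in SAP 5.3.1 is limited in scope: "For the time-to-event variables, in case of death prior to the event, the subject will be censored". By contrast, the hospital recovery scale (HRS, SAP 5.2.1) and the fundamental HRS (SAP 5.3.1.1) both make death the worst category. The HRS is also set to missing once a subject withdraws alive.

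**Total stay.** Protocol 2.1.2 lists "Time from start of study drug to hospital discharge and total length of hospital stay". SAP 5.3.1.1 defines the total in words as hours spent in hospital from first intake to study termination. The bracketed formula is the end of hospitalization minus first intake, summed over every separate stay. Later, the same cell says first intake replaces the start of a stay only if that stay began earlier. The rows for ICU time, ventilation time and antibiotic duration each subtract the episode's own start, and each describes its derivation as analogous to total hospital stay.

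**The concern.** The Day 6 coding contradicts both its own title and the protocol endpoint. Neighbouring incidence rows (readmission, mortality, antibiotic use) code the named event as Yes. A program that follows the row would tabulate and model the opposite event.

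Correcting the labels alone is not enough. A subject who died on Day 3 is literally out of hospital for the whole of Day 6 and stays in the denominator, so that death would then count as a success. Withdrawals before Day 6 have no rule either.

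The stay formula contradicts the sentence that defines it and the start rule in its own cell. It is correct for a subject with one stay that began before first intake. It fails for anyone readmitted.

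Both are protocol secondary endpoints. Neither is among the seven endpoints in the confirmatory strategy (SAP 5.1.1).

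**Working it through.** **Planning inputs (SAP 1.4).** Placebo Day 6 distribution 30/30/25/5/5/5%, common odds ratio 0.62 (a 38% reduction), 600 subjects 1:1, 90% power; two-sided 5% from SAP 5.1.1.

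The pimodivir distribution comes from dividing the placebo odds of being in a category or better by 0.62. For category 1: (0.30/0.70)/0.62 = 0.691, and 0.691/1.691 = 0.4087. The full set is 0.4087, 0.2988, 0.1938, 0.0342, 0.0328, 0.0316.

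The plan's own figure reproduces. With the proportional-odds formula N = 12(z₀.₉₇₅ + z₀.₉₀)² / [ln(0.62)² (1 − Σp̄³)], the result is N = 601.4, and power at 600 is 89.9%.

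**Day 6 endpoint.** The documents give no rate for physical absence on Day 6, so HRS category 1 is the proxy: 30.0% placebo, 40.9% pimodivir. That category also includes inpatients judged ready for discharge. Let d be placebo mortality, dₜ = 1/(1 + ((1−d)/d)/0.62) the pimodivir mortality, and f the share of deaths before Day 6. If these deaths count as out of hospital, the proportions become 0.30 + d·f and 0.4087 + dₜ·f. Here dₜ is 0.62%, 1.25% and 3.16% for d of 1%, 2% and 5%. Mortality below 5% and its timing are assumptions. Power is a two-sided 5% Wald test on the log odds ratio with 300 per arm.

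| Deaths counted as out of hospital | Placebo | Pimodivir | OR | Power |
|---|---|---|---|---|
| None (deaths handled) | 30.0% | 40.9% | 1.61 | 79% |
| d = 1%, all before Day 6 | 31.0% | 41.5% | 1.58 | 76% |
| d = 2%, all before Day 6 | 32.0% | 42.1% | 1.55 | 73% |
| d = 5%, half before Day 6 | 32.5% | 42.5% | 1.53 | 71% |
| d = 5%, all before Day 6 | 35.0% | 44.0% | 1.46 | 62% |

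The last row moves 300 × 5% = 15 placebo deaths and 300 × 3.16% ≈ 9.5 pimodivir deaths into the favourable group.

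The label effect alone, with deaths handled, is 1/1.613 = 0.62. With the reversed labels and all 5% deaths counted as out of hospital, it is 1/1.461 = 0.68. Reversing the labels leaves the two-sided p-value unchanged.

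**Total stay, worked example.** First intake on Day 1; in hospital Days 1-5 and Days 15-18.
- Correct: (5 − 1) + (18 − 15) = 7 days.
- Printed: (5 − 1) + (18 − 1) = 21 days.
- Excess: 14 days = 10 at home + 4 from the first stay counted again.

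In general, each readmission adds an excess equal to its own start minus first intake.

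**Total stay, effect on the comparison.** The documents give no readmission rates or timings. Assume readmission starts 9-19 days after first intake (midpoint 14) and lasts 2-6 days. Readmission of 5% or 10% then raises an arm's mean by about 0.05 × 14 = 0.7 or 0.10 × 14 = 1.4 days.

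The planned Hodges-Lehmann difference (pimodivir minus placebo) was simulated with 400 runs and 300 per arm. The index stay was log-normal (sigma 0.6), with 30.0%/40.9% out within 5 days and a 27-day cap.

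| Readmission, placebo / pimodivir | Correct formula (days) | Printed formula (days) |
|---|---|---|
| 5% / 5% | −1.04 | −1.03 |
| 10% / 10% | −1.05 | −1.04 |
| 10% / 5% | −1.19 | −1.36 |
| 5% / 10% | −0.86 | −0.67 |

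**The case against.** The strongest reply is that the intent is recoverable. The Day 6 row describes both states in words, the SAP introduction says it is to be read with the protocol, and the protocol fixes the endpoint. The stay cell opens with hours in hospital, and its start rule would be redundant if first intake were always subtracted. The sister rows show the intended form. The programs may also follow separate presentation specifications that are not among these documents.

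Death on Day 6 is handled elsewhere. The primary endpoint's split of not hospitalized versus worse (SAP 5.2.3) handles it. So does the fundamental HRS, which is analysed daily "with Day 6 excluded for the HRS and including Day 6 for the fundamental HRS". Mortality is reported overall and per day. The Day 6 row is silent on death; it does not direct that deaths count as discharges.

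Finally, power is a weak yardstick for an endpoint that is only to be investigated. The stay shifts also need an assumed two-fold imbalance in readmission. At 0.17 to 0.19 day, they are about half the estimator's sampling standard deviation of roughly 0.33 day.

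Most of this stands and keeps the point minor. It does not remove it. SAP 5.3.1 presents these tables as the formulae to be used, and the printed ones give wrong values. Nothing in the documents settles how deaths or withdrawals are classified in the Day 6 row.

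**Conclusion.** Both derivations are wrong as written and should be corrected; the severity is minor.

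The label reversal inverts the Day 6 categories and the direction of the odds ratio. The missing death rule would pull the odds ratio from 1.61 to somewhere between 1.58 and 1.46 over the mortality range examined. The lower end requires all of the SAP's 5% placebo mortality to fall before Day 6. The only death reported in the earlier hospital study was at Day 8 (Protocol 1.1, Clinical Safety), so the real effect may be small.

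The stay error is large for an individual readmitted subject (21 days against 7 in the example). It is about 0.01 day on the planned Hodges-Lehmann difference if readmission is equal between arms, and it becomes noticeable only if readmission differs. These sizes rest on proportional odds, the category 1 proxy, and assumed mortality timing and readmission patterns.

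The primary endpoint, the confirmatory sequence and the sample size are not affected.

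**What to change.** 1. **Day 6 row.** Code Yes as alive and not in hospital at any time on Day 6. Code No as in hospital for any part of Day 6, or dead on or before Day 6. Treat subjects who withdrew alive before Day 6 as missing, as the HRS does, and state this as an exception to the denominator rule in SAP 5.3.2.1; or state another rule. This gives the same split as fundamental HRS category 1 versus worse, provided the same withdrawal rule is written for that scale, whose row gives none. The SAP should note that the result will still differ from the HRS split for inpatients judged ready for discharge.
2. **Total stay row.** Replace the formula with the sum over stays of [end of stay − max(start of that stay, first intake)].

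The cost is two edits to SAP derivation text and the matching programs, preferably before unblinding. There is no protocol change, no new data and no change to the confirmatory testing.
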